The study will use a double-blind placebo controlled design. Intranasal OT (n=12) or PBO (n=12) sprays will be administered at 11:30 am, approximately 45 min prior to the scanning session. This dose and timing of OT administration were selected based on the literature [17, 18]. ***MIST Procedure:*** The study will use a block design of three, 6-min runs separated by 2-min of rest for feedback, for a total of 24 min. During each run, participants will be exposed to 40-sec blocks of three different conditions (rest, control, and experimental). Prior to the task, participants will be shown images of what the screen will look like during each condition. The participants will be instructed to relax during the rest condition and focus on the screen. During the control condition, the participants will be asked to answer math problems as accurately as possible but will also be told that their responses will not be recorded. During the experimental condition, the participants will be asked to perform the math task as quickly and accurately as possible. A performance bar located on the screen will allow them to see their performance as compared to an “average” person. The participants will be told that the average person would answer about 85% of the problems correctly; however, the program limits the participants’ performance rate to between 35-45%. A time limit will be enforced throughout the experimental condition. After each run, the participants will be given negative feedback from the investigator. ***BOLD-fMRI Procedure:*** Data will be acquired on a Siemens Trio 3T scanner in MUSC’s Center for Biomedical Imaging. For co-registration and normalization of functional images, a high resolution T1-weighted MPRAGE anatomical image will be acquired with the following parameters: TR= 2100 ms, TE= 4.18 ms, flip angle= 12°, field of view= 256 mm, slice thickness= 1.0 mm. The scanning planes will be oriented parallel to the anterior commissure–posterior commissure line. Participants will be asked to relax and keep their eyes opened and fixed on a cross-hair for 6 min while resting state data are collected. Participants will then complete the MIST. T2*-weighted gradient-echo planar images (EPI) will be acquired with the following parameters: TR= 2000 ms, TE= 27 ms, flip angle= 76°, matrix 64 x 64, field of view= 23 cm, slice thickness= 3.7 mm with no gap, with 36 slices to cover the entire

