brain. ***Implicit Facial Affect Recognition Task:*** The amygdala response to emotional faces that are presented outside the focus of attention (i.e. implicit tasks) is significantly greater than that observed during overt (explicit) presentation of the same stimuli [25]. Emotional adult faces will be selected from a variety of sources are standardized in size and enclosed in the same oval surround [26]. [name] (MUSC) has developed a corpus of faces for a recent project (National Institute of Mental Health, R21 MH086958-01, “A comparative developmental connectivity study of face processing”) that will be used for the present project. The faces will depict male and female Caucasian, Asian and African Americans expressing three different categories of emotion; fear, anger, and happiness. Neutral faces will also be presented (Figure 5). Because the participants will also be from different ethnic categories, it is important to include a mixture of races. In a block design, participants will view a series of faces (for 27.5 sec) within a block and report on the gender of those faces at the end of the block (for 5 sec). Each block will present 56 faces that depict the same emotion and same gender so there will be 6 pseudorandomly ordered task blocks (3 emotions x 2 genders) and 7 rest blocks (27.5 sec each) that present a crosshair to be fixated. In each task block, each emotional face will be presented for 33 msec. followed by a neutral face mask (from a different individual) for 167 msec. followed by a blank screen for 291 msec. At the end of the block participants will report the gender using two buttons on a response pad. Assignment of face sets to sessions will be counterbalanced across subjects.

Payment to Participants: Participants will receive \$100 for completing the scanning visit.

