Data Analyses *MIST:* Post-acquisition preprocessing and statistical analysis of all of imaging data will be performed using FEAT (FMRIB Expert Analysis Tool) Version 5.98, part of FSL (FMRIB's Software Library). Data will be preprocessed using scripting tools from FMRIB Expert Analysis Tool (FEAT). Functional connectivity will be measured using a PPI seed-based approach [19]. A customized square wave-form representing the task and the duration of each condition will be convolved with a double-gamma hemodynamic response function. A mask of the seed region will be made using a 12-mm diameter sphere located in the center of the amygdala using the MNI coordinates (x, y, z = ±22, 0, -22). For each participant, the mean corrected and high pass filtered time series of the BOLD signal in the amygdala will be extracted and used in a single subject whole brain PPI analysis. The PPI model will include (1) the task vector; (2) the time series of the BOLD signal in the amygdala; (3) a term representing the positive task x seed interaction; and (4) a term representing the negative task x seed interaction. The first level analysis will generate contrast images of the parameter estimates for each of the four regressors. Since the hypotheses explore increases in corticolimbic connectivity, the group analysis will focus on the positive interaction term. The contrast images of the parameter estimates of the positive interaction term will be entered into a 2nd level random effects analysis. Unpaired t-tests will be used to test for group differences. All group level results will be thresholded at $Z > 2.3$ using a corrected cluster threshold of $p = 0.05$. A linear mixed effects model containing all serially measured time points will be used to assess the effects of OT versus placebo on alcohol craving and anxiety ***Implicit Facial Affect Recognition Task:*** Following preprocessing (described above), within-task data from individual participants will be analyzed with a fixed-effects general linear model (GLM), with each emotion (described below) modeled as a box-car function convolved with a double-gamma hemodynamic response function. The response period at the end of each block will also be modeled as a separate variable to remove effects of explicit decision making and response selection. The GLM procedure is repeated for each voxel with six movement parameters (3 rotation values in radian and 3 translation values in millimeter) included as covariates to control for the influence of head motion on the data. Following first-level analysis, subject-specific contrasts will be entered into second-level, random-effects analyses. Since the hypotheses associated with Specific Aim 2 explore amygdala activity, we will use a region of interest approach (ROI). The BOLD signal from the left amygdala will be extracted using an anatomical mask generated by a 12-mm diameter sphere located in the center of the left amygdala using the MNI coordinates (x, y, z = -22, 0, -22). The percent signal change between the fearful and neutral conditions (contrast of interest) will be calculated for each participant. Separate random-effects one-way analysis of variance tests (ANOVA) will be used to test for the following group differences (AUD-PBO vs. AUD-OT). Since human neuroimaging studies have found that other brain regions play a role in implicit emotional processing, including the right amygdala and insula [27,28], secondary analyses will also include these regions. In addition, OT may impact amygdala responding to happy faces [29] therefore group differences in amygdala responding in the happy-neutral contrast may be explored in future

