1. RISKS TO THE SUBJECTS

1.1 Human Subject Involvement and Characteristics

Admission into the study is open to men and women and to all racial and ethnic groups, age 21-40 with alcohol use disorder. Participants will be recruited through the Medical University of South Carolina's (MUSC) Addictions Research Center (ARC) Assessment Core. Inclusion/exclusion criteria are listed below:

General Inclusion/Exclusion Criteria

Inclusion Criteria

1. Age 21-40.
2. Subjects must be able to provide informed consent and function at an intellectual level sufficient to allow accurate completion of all assessment instruments.
3. Meets the DSM-5 criteria for current alcohol use disorder.
4. Reports drinking on average, at least 20 standard alcoholic drinks per week for at least the past three months.
5. Currently not engaged in, and does not want treatment for, alcohol related problems.
6. Lives within 50 miles of the study site.
7. Subjects must consent to random assignment.
8. Able to maintain abstinence for two days (without the aid of detoxification medications) as determined by self-report and breathalyzer measurements. Subjects must also have a negative breathalyzer urine drug screen at the study visit.
9. Subjects must consent to the study visit which includes an outpatient admission to the Addiction Sciences Division and completing one functional magnetic resonance imaging (fMRI) scanning session.

Exclusion Criteria

1. Currently meets DSM-5 criteria for any other psychoactive substance use disorder.
2. Is determined
3. Any psychoactive substance use (except marijuana and nicotine) within the last 30 days by self-report and urine drug screen. For marijuana, no use within the last seven days by verbal report and negative (or decreasing) urine THC levels.
4. Meets DSM-5 criteria for current major depression, panic disorder, obsessive-compulsive disorder, post-traumatic stress syndrome, bipolar affective disorder, schizophrenia, dissociate disorders, eating disorders, and any other psychotic disorder or organic mental disorder.
5. Has current suicidal ideation or homicidal ideation.
6. Has the need for maintenance or acute treatment with any psychoactive medication including anti-seizure medications and medications for ADHD.
7. Is currently taking medication known to affect alcohol intake (e.g., disulfiram, naltrexone, acamprosate, topiramate).

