5. DATA AND SAFETY MONITORING PLAN (DSMP)

5.1 Summary of the Protocol

The primary objective of this proposal is to identifying the neurobiologic substrates of social stress in individuals with alcohol use disorder. Individuals with alcohol use disorder will receive either intranasal oxytocin (24 IU) or a placebo spray prior to participating in a single fMRI scanning session. During the scanning session participants will complete the Montreal Imaging Stress Task, a Facial Affect Recognition Task, and a resting state scan. The primary outcomes of interest are (1) corticolimbic functional connectivity at rest; (2) corticolimbic functional connectivity during the MIST and (3) subjective anxiety and craving responses to the MIST.

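### Face sets are counterbalanced over sessions, but each participant has one scan: set becomes an unmodelled between-person nuisance in the face task (minor)

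*Combined protocol and SAP*

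**What the plan says.** The last sentence on the Implicit Facial Affect Recognition Task (Approach) reads "Assignment of face sets to sessions will be counterbalanced across subjects". The number of sets is not given. The task is described as one sequence of six task blocks and seven rest blocks, with no second run or visit.

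The rest of the protocol describes one scan per person:

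- Section 1.1, inclusion criterion 9, requires "completing one functional magnetic resonance imaging (fMRI) scanning session".
- Section 5.1 has participants receive OT or placebo "prior to participating in a single fMRI scanning session".
- The Approach describes parallel arms: "Intranasal OT (n=12) or PBO (n=12) sprays will be administered at 11:30 am".

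On allocation, section 1.1 says "Subjects must consent to random assignment". No method, blocking or stratification is given, and nothing links allocation to face set.

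Under Data Analyses, the face-task outcome is one value per participant: left-amygdala percent signal change between the fearful and neutral conditions. The arms are compared by one-way ANOVA on group alone. The covariate rule that closes Data Analyses covers only baseline characteristics on which the groups differ significantly.

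**The concern.** Counterbalancing sets over sessions belongs to a repeated-session design. There, each person sees every set and differences between sets cancel within the person. With one session per person there is no order to counterbalance, and that benefit is lost.

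Staff would have to interpret the sentence. The nearest workable reading is that some participants see one set and some another. Set then varies between people, in an analysis that compares people. The sentence asks for balance over subjects and does not mention arm. The ANOVA has no term for set, and the covariate rule does not reach it, because set is a feature of the task and not a baseline characteristic.

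At stake is the precision of the OT v PBO comparison in the face task and, with 12 per arm, its exposure to an uneven split of sets between arms.

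**Working it through.** The documents give no power or effect-size figure for this task, so there is none to reproduce.

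**Inputs from the documents.** 12 participants per arm, 24 in total; one session each; one fearful-v-neutral value each; group-only ANOVA.

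**Assumptions (not in the documents).** Two sets, each shown to 12 of the 24 participants and assigned without regard to arm. Set effect *s* on the fearful-minus-neutral contrast of 0.25, 0.5 or 1.0 within-set SD.

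**1. Could sessions mean runs?** The three runs in the Approach belong to the stress task (MIST). The face task is a single sequence of blocks, so that reading does not restore within-person cancellation.

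**2. Chance imbalance.** Let X be the number in the OT arm who see set A. X is hypergeometric: P(X = k) = C(12,k)² / C(24,12), with C(24,12) = 2,704,156.

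- P(6:6) = 853,776 / 2,704,156 = 0.316
- P(7:5 either way) = 2 × 627,264 / 2,704,156 = 0.464
- P(8:4 or worse) = 1 − 0.316 − 0.464 = 0.220
- P(9:3 or worse) = 0.220 − 2 × 245,025 / 2,704,156 = 0.220 − 0.181 = 0.039

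**3. Shift in the arm difference.** Shift = s × [X/12 − (12 − X)/12] = s × (2X − 12)/12. Its mean is 0. Var(X) = 12 × ½ × ½ × 12/23 = 1.565, so the SD of the shift is s × 2 × √1.565 / 12 = 0.21 s.

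| Set effect (SD) | Shift at 8:4 (s × 4/12) | Shift at 9:3 (s × 6/12) |
|---|---|---|
| 0.25 | 0.08 | 0.13 |
| 0.5 | 0.17 | 0.25 |
| 1.0 | 0.33 | 0.50 |

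The standard error of the arm difference is √(2/12) = 0.41 SD.

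**4. Overall error rate and power.** Under these assumptions, simulation with a two-sided 5% t-test (equivalent to the two-group ANOVA; 400,000 runs) gives an overall false-positive rate of about 0.05 at each set effect. At s = 0.5 the rate is about 0.06 given an 8:4 split and about 0.04 given 6:6, and these average out.

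The cost appears as variance. With an even split, the within-arm SD is multiplied by √(1 + s²/4): 1.03 at s = 0.5 and 1.12 at s = 1.0. Power for a true 1 SD group effect is 0.65 with one common set (noncentral t, 22 df, noncentrality 1/0.408 = 2.45). It falls to 0.62 at s = 0.5 and 0.55 at s = 1.0 when sets are ignored.

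**5. What cancels.** The outcome is a difference between two conditions in the same person. A set effect common to both drops out, and only a set effect that differs between fearful and neutral faces remains. This presumes that both conditions draw on the same set, which the documents do not state.

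**6. After the fix.** With one common set, or two sets split 6:6 in each arm, 2X − 12 = 0 and the shift is 0 at any *s*.

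**The case against.** A reader might infer that the rule biases the OT v PBO comparison. The documents do not support that. Nothing suggests that sets would be assigned in a way related to treatment. If they are assigned independently of it, the expected shift is zero and the test keeps its overall 5% error rate. Quoting only the raised false-positive rate after an unlucky split would mislead, because even splits lower it by way of compensation. This objection stands.

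A reader might also infer that the instruction is impossible to follow. That is too strong. There are 24 sessions in all, and sets can be spread over them in balanced numbers. The sentence is ill-fitting and ambiguous, but it can be acted on. It also does not say that arm is to be ignored; balance within arm is simply left unstated.

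The size is assumed throughout. The documents give neither the number of sets nor a set effect. The faces are standardized in size and surround, and the contrast removes any effect common to both conditions, so the residual effect could be small.

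Finally, section 5.1 does not list the face task among its three primary outcomes, and the task does not appear in Aims 1 and 2 as stated at the start of the protocol. Resting-state connectivity, MIST connectivity, and craving and anxiety are untouched.

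These points limit the size and priority of the concern. They do not remove the mismatch between the rule and the one-session design, or supply any handling of set in the prespecified group test.

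**Conclusion.** The point holds as a minor one. The face-set rule does not fit a design with one session per person and gives no within-person cancellation. On its nearest workable reading, face set is a between-person nuisance that the plan neither balances within arm nor models. The consequence is added noise and possible chance imbalance, not systematic bias.

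The size rests on the assumed two sets, the 12/12 use and the assumed set effects. At a set effect of 0.5 SD the loss is about 3 points of power for a 1 SD group effect; at 1.0 SD it is about 10 points. Roughly one trial in five would have a split of 8:4 or worse. If only one set is used, or sets are in practice balanced within arm, the shift is zero.

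**What to change.** Replace the counterbalancing sentence with a statement that all participants view the same face set in their single session.

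If several sets are to be kept, state how many, assign them in equal numbers within each arm through the blinded allocation list, and add set as a factor in the face-task group model. Either version answers the concern.

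The cost is one sentence in the protocol, plus one model term in the second version. There are no extra participants, staff or scan time. A single set narrows the stimulus sample slightly. Modelling set uses one degree of freedom for two sets and a few for more. With two balanced sets, error df go from 22 to 21, and power for a 1 SD effect stays at 0.65 (noncentral t, noncentrality 2.45).

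### The MIST connectivity model, which yields a primary outcome, lists no head-motion terms although the face-task model has six; motion that differs by condition and by arm would bias it

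*Combined protocol and SAP*

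**What the plan says.** The MIST paragraph of Data Analyses enumerates the first-level model. It opens with "The PPI model will include (1) the task vector; (2) the time series of the BOLD signal in the amygdala" and ends with "3) a term representing the positive task x seed interaction; and (4) a term representing the negative task x seed interaction". The next sentence confirms the count: "The first level analysis will generate contrast images of the parameter estimates for each of the four regressors". The positive interaction estimate then goes into an unpaired t-test between arms. The preprocessing statement is general and names no motion step: "Data will be preprocessed using scripting tools from FMRIB Expert Analysis Tool (FEAT").

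The face-task paragraph starts from the same preprocessing but goes further: "The GLM procedure is repeated for each voxel with six movement parameters (3 rotation values in radian and 3 translation values in millimeter"), which are "included as covariates to control for the influence of head motion on the data".

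Section 5.1 names "corticolimbic functional connectivity during the MIST" among the primary outcomes. The face task is not in that list. The covariate rule that closes Data Analyses is confined to baseline characteristics. No section gives a motion limit, a censoring rule or a comparison of motion between arms for any scan.

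**The concern.** The written safeguard against head motion covers the task that is not a primary outcome and omits the one that is.

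The omission matters because of the task design. Under MIST Procedure, the control blocks ask for accuracy and tell participants that answers are not recorded. In the experimental blocks, "the participants will be asked to perform the math task as quickly and accurately as possible", under an enforced time limit. Head motion may therefore differ between the two conditions whose contrast defines the interaction. Motion that reaches both seed and target adds shared signal. If there is more of it in stress blocks, the seed-target slope rises in those blocks, and that change is what the interaction term estimates. If the increase also differs between oxytocin (OT) and placebo (PBO), the group test reads it as a treatment difference in coupling.

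**Working it through.** **1. The two models side by side**

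| | MIST | Face task |
|---|---|---|
| Primary outcome in section 5.1 | yes | no |
| Preprocessing | FEAT, steps not itemised | the same |
| Movement terms in first-level model | 0 (four terms listed) | 6 |

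The six covariates are thus additional to whatever the shared preprocessing does.

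**2. Cost in degrees of freedom.** Each run lasts 6 min at TR 2 s: 360 / 2 = 180 volumes. Four listed terms and an intercept leave 180 - 5 = 175 residual degrees of freedom. Six movement terms leave 169. Over three runs the cost is 18 of 525.

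**3. When motion biases the interaction.** All values here are assumptions. Seed and target noise have variance 1, baseline coupling is 0.2, and a shared motion artefact has SD 0.4, multiplied by *a* in stress blocks. The slope of target on seed within a condition is

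(0.2 + 0.16a²) / (1 + 0.16a²)

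- a = 1.0: 0.36 / 1.16 = 0.310
- a = 1.5: 0.56 / 1.36 = 0.412
- a = 2.0: 0.84 / 1.64 = 0.512

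With stress coded +1 and control -1, the interaction slope is about half the stress-minus-control difference: 0, 0.051 and 0.101. Two results follow. If *a* is the same in both arms, the bias cancels between arms. If PBO has a = 2.0 and OT has 1.5 or 1.0, the spurious OT minus PBO difference is about -0.05 or -0.10. The simulation below gave -0.040 and -0.078: the same sign and order. The closed form ignores haemodynamic lag.

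**4. Illustrative simulation.** Settings: 12 v 12, 3 runs x 180 volumes, between-subject slope SD 0.05, one target region, one interaction term, two-sided t-test at 0.05, 250 trials per row (Monte Carlo SE at most √(0.25/250) = 3.2 points).

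No true effect, rejection rate:

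| Stress motion, PBO v OT | Artefact linear in the six parameters | No movement terms | Six terms |
|---|---|---|---|
| 1.5 v 1.5 | all | 6% | 4% |
| 2.0 v 1.5 | all | 30% | 6% |
| 2.0 v 1.0 | all | 81% | 5% |
| 1.0 v 2.0 | all | 81% | 5% |
| 2.0 v 1.5 | half | 37% | 16% |
| 2.0 v 1.0 | half | 82% | 38% |
| 1.0 v 2.0 | half | 84% | 45% |

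Without movement terms, no rejection favoured OT when PBO moved more, and every rejection favoured OT when OT moved more.

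True OT > PBO slope difference of 0.08, power in that direction:

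| Stress motion, PBO v OT | Artefact linear | No movement terms | Six terms |
|---|---|---|---|
| 1.0 v 1.0 | all | 69% | 65% |
| 2.0 v 1.0 | all | 2% | 74% |
| 2.0 v 1.0 | half | 1% | 8% |

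**5. A scale that does not depend on the motion model.** For an unpaired t-test with 12 per arm (noncentrality d√6), a spurious standardised difference of 0.25, 0.5, 0.75 or 1.0 is declared significant in 9%, 22%, 42% or 65% of trials instead of 5%.

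**The case against.** - **The list may not be exhaustive.** The plan says what the model will include and which contrast images it produces; nuisance terms need no contrast image. FEAT preprocessing may also include realignment. Both readings are possible. But the face task shares that preprocessing and its movement terms are written out, so their absence for the MIST cannot be taken as implied. On the kindest reading, a primary model is ambiguous and needs the same sentence.
- **The seed regressor already absorbs shared motion.** This stands for motion that is constant across conditions. The outcome is an interaction slope, not a simple correlation between two regions, so it is wrong to say that shared motion inflates it directly. Bias in the group test needs motion that differs by condition and by arm. With equal stress motion, rejection stayed near nominal.
- **Nothing shows that motion will differ by arm.** This also stands. A reader might infer it from Hypothesis 1B, since a calmer OT group might move less. That hypothesis concerns self-reported anxiety and craving. The documents do not link anxiety to head movement, both conditions require answering sums, and assignment is random and double-blind. Arm-dependent motion is plausible but not shown. Randomisation balances the tendency to move only in expectation, and it cannot remove an effect of the spray on motion after dosing.
- **The remedy is imperfect.** The near-nominal rates with six terms hold only if the artefact is linear in them. With half of it linear, they reach 16% to 45%.

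**Conclusion.** The omission is clear from the text, and correcting it is a cheap improvement to a primary analysis. The consequence is conditional: stress-locked motion must differ between arms. The documents give no motion data, so its size is unknown. The simulated rates show direction only; they rest on assumed artefact strength and motion ratios, and on a single region rather than the plan's whole-brain cluster threshold.

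Direction matters. A reader might take the omission to mean that a false finding in favour of OT is likely. The documents do not support that. If PBO participants move more under stress, the error runs against Hypothesis 1A, by masking a real effect or producing a spurious PBO > OT difference. A false OT > PBO result would need more stress-locked motion under OT, for which the plan gives no reason.

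**What to change.** Before unblinding, add the six movement parameters already specified for the face task to each MIST run's first-level connectivity model. Add one nuisance regressor for each volume above a motion limit fixed in advance. Report motion by arm and by MIST condition. If these terms were always intended, state so in the MIST paragraph.

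A group test adjusted for each participant's stress-minus-control motion may be reported as a sensitivity analysis only. That motion is measured after dosing, and adjusting for it could remove part of an OT effect.

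Cost: a few sentences and an edit to the design files, with no change to visits or scans. Beyond the degrees of freedom shown above, each flagged volume costs one more. Some real stress-locked signal may be removed, and correction will be incomplete where the artefact is not linear in the parameters. The per-volume regressors are meant to reduce that last problem but may not remove it.

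### The nominal 5% error of the whole-brain MIST connectivity map is not assured at Z > 2.3 if the cluster correction is parametric; permuting the treatment labels would secure it cheaply

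*Combined protocol and SAP*

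**What the plan says.** The rule is in the MIST part of Data Analyses. The amygdala time series is "used in a single subject whole brain PPI analysis". The images for the positive interaction term are then "entered into a 2nd level random effects analysis", and "Unpaired t-tests will be used to test for group differences". All group-level maps are formed at Z > 2.3, "using a corrected cluster threshold of" p = 0.05. The software is "FEAT (FMRIB Expert Analysis Tool) Version 5.98, part of FSL".

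The study design paragraph gives the arm sizes: "Intranasal OT (n=12) or PBO (n=12) sprays will be administered at 11:30 am". On direction the plan says: "Since the hypotheses explore increases in corticolimbic connectivity, the group analysis will focus on the positive interaction term". It does not say whether the group contrast is one- or two-sided.

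The map serves Hypothesis 1A under Aim 1 (oxytocin above placebo for amygdala coupling with orbitofrontal and anterior cingulate cortex). Section 5.1 lists connectivity during the MIST as one of three primary outcomes. The plan does not name the cluster-inference method, the smoothing kernel or the second-level estimator. It sets a region of interest for the faces task but none for the MIST.

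**The concern.** A parametric cluster correction asks how large a cluster above the forming threshold would be by chance, given the smoothness of the noise. Smoothness is estimated from neighbouring voxels. If the noise also has weak correlation over longer distances, neighbouring voxels hardly show it, yet it makes large chance clusters more common. The effect is strongest at a low forming threshold, where clusters are large.

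The corrected 5% is the only stated error control on the MIST map. If the true rate is well above 5%, a significant oxytocin-placebo cluster from 24 participants is weaker evidence than its p-value implies, and nothing in the planned output would show this.

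**Working it through.** **The plan's own figure.** The 5% is a setting and cannot be reproduced, because the documents give no kernel, smoothness, spatial autocorrelation or cluster method. What can be tested is whether a rule of this kind keeps 5% under stated noise shapes.

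**Inputs from the documents.** 12 v 12, so 24 - 2 = 22 df; unpaired t; whole-brain search; Z > 2.3, a one-sided voxel p of 1 - Phi(2.3) = 0.0107; in-plane voxel size 230/64 = 3.6 mm; slices 3.7 mm.

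**Assumptions.** Parametric random-field inference; ordinary t-tests without first-level variance weighting; stationary noise; an ellipsoid for the brain; the noise shapes below.

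**Formula.** For V voxels, threshold z and estimated FWHM f in voxels (equal in the three directions for illustration):
- expected clusters: E = V x [(4 ln 2)^1.5 / f^3] x (z^2 - 1) x exp(-z^2/2) / (2 pi)^2
- expected voxels above threshold: N = V x (1 - Phi(z))
- beta = [Gamma(2.5) x E/N]^(2/3)
- corrected p for a cluster of k voxels: 1 - exp(-E x exp(-beta x k^(2/3)))

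**Example.** Semi-axes of 70, 85 and 60 mm give (4/3) x pi x 70 x 85 x 60 = 1,495,398 mm3. Divided by 3.6^3 = 46.656 mm3, this is about 32,050 voxels. With estimated FWHM 7.9 mm, f = 7.9/3.6 = 2.19. At z = 2.3, E is about 108, N = 32,050 x 0.0107 = about 344, and beta = (1.329 x 108/344)^(2/3) = about 0.559. Setting p = 0.05 gives k = [ln(108/0.0513)/0.559]^1.5, about 51 voxels. Smoothness enters only through f, so long-range correlation that leaves f almost unchanged leaves this cut-off almost unchanged.

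**Null simulations.** Three sets were run, with error counted per direction over the whole brain.

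Set 1: 3.6 mm grid, 300-320 runs x 2 directions. The long-tailed autocorrelation is a x exp(-r^2/(2 x 3.4^2)) + (1 - a) x exp(-r/c), with r and c in mm.

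| Noise | Estimated FWHM (mm) | Z > 2.3 | Z > 3.1 |
|---|---|---|---|
| Gaussian, 8 or 12 mm | 7.9 or 11.7 | 2.0-2.2% | 1.3-1.6% |
| a = 0.95, c = 10 | 5.6 | 4.2% | 1.6% |
| a = 0.9, c = 10 | 5.7 | 8.0% | 2.5% |
| a = 0.8, c = 10 | 5.8 | 16% | 2.5% |
| a = 0.7, c = 10 | 5.9 | 27% | 4.5% |
| a = 0.5, c = 10 | 6.2 | 48% | 7.2% |
| a = 0.8, c = 6 | 5.5 | 9.5% | 2.0% |
| a = 0.5, c = 6 | 5.5 | 32% | 5.0% |
| a = 0.65, c = 15 | 6.3 | 41% | 7.5% |
| a = 0.5, c = 15 | 6.7 | 53% | 10.8% |

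Monte Carlo SE is about 0.6 points near 2% and 2 points near 30-50%. Along the c = 10 mm rows, error at Z > 2.3 rises from 4.2% to 48% while estimated smoothness moves by only 6.2 - 5.6 = 0.6 mm. Counting a cluster in either direction, the range at Z > 2.3 is about 4% to 82%.

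Set 2: 2.5 mm grid, 120-200 runs, SE about 2-4 points. Gaussian 8 mm noise gave 3.8% at Z > 2.3 and 2.5% at Z > 3.1. With 30% of the variance in a 20 mm component the figures were 27% and 2.5%; with 50%, 33% and 8.3%. Mean estimated FWHM was 7.8, 8.1 and 9.3 mm.

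Set 3: 80 runs per shape, one direction. Gaussian noise gave about 1%; three increasingly long-tailed shapes gave 14%, 30% and 51%. On the shape where the parametric rule gave 30%, permuting the labels gave about 5% (40 runs; SE = sqrt(0.05 x 0.95/40) = 3.4 points).

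**Power check (set 2 noise).** For an assumed effect of d = 1.2 in a 10 mm radius, detection at Z > 2.3 v Z > 3.1 was 86% v 81% (Gaussian), 75% v 74% (30%) and 49% v 64% (50%).

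**The case against.** The plan fixes a multiplicity-corrected threshold in advance, which is reasonable for a 24-person pilot, and under Gaussian noise the rule is conservative. The documents never call the correction parametric; that is read from the software and the form of the threshold. The simulations use a simplified brain and assumed noise. All of this stands, and it limits what can be claimed.

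A reader might infer more than the documents support:
- *That the true error is about 25-35%.* Only some assumed shapes give this, such as a = 0.7 with c = 10 mm. Nothing in the documents places this trial's noise within the simulated range.
- *That 5% holds only for exactly Gaussian noise.* A mild departure (a = 0.95, c = 10 mm) stayed at 4.2%.
- *That these rates are the chance of falsely confirming Hypothesis 1A.* They count a false cluster anywhere in the brain. A cluster outside the two named regions does not support 1A, so the relevant chance is lower; it was not computed.
- *That Z > 3.1 cures the problem.* It still gave 8.3% and 10.8% under the most long-tailed shapes.

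What remains is that the plan has no safeguard against long-range correlation and that routine smoothness estimates would barely show it.

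**Conclusion.** The point holds as a sensitivity, conditional on parametric random-field inference: the nominal 5% is not assured at Z > 2.3. Simulated whole-brain error per direction was about 1-4% with Gaussian noise and about 4-53% with assumed long-tailed noise. The direction of the effect is consistent across three sets of simulations with different settings. Its size in this trial is unknown, because the documents give neither smoothness nor noise shape. They do not support the conclusion that the planned map is invalid. This is a worthwhile, inexpensive improvement to the analysis of one of three primary outcomes.

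**What to change.** Name the cluster-inference method, the smoothing kernel, the second-level estimator and the sidedness of the contrast. On the same second-level contrast images, replace the parametric cluster p with permutation of the OT/PBO labels, using the maximum-cluster or threshold-free statistic at family-wise p < 0.05. The inclusion criteria in section 1.1 require consent to random assignment, and randomisation justifies the permutation without a spatial noise model. With 12 v 12 there are 24!/(12! x 12!) = 2,704,156 labellings, so a random sample of them is enough. The permutations should follow the actual allocation scheme.

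If parametric inference is kept, Z > 3.1 reduces the inflation, and the plan should state that up to about 8-11% error per direction remained in simulation under the most long-tailed shapes.

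The cost is a short edit to the analysis section and some computing time; no new data are needed. The downside is that diffuse, low-amplitude clusters that would have passed at Z > 2.3 may no longer be called significant.
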